## 6.2.1 Primary Efficacy

### 6.2.1.1 Primary Efficacy Variable

The primary efficacy variable is the time (in days) from randomization to the first occurrence of the following primary efficacy outcome events:

- Myocardial infarction
- Stroke
- Cardiovascular death

All unrefuted primary efficacy outcome events within the data scope according to intention-to-treat principle (see Section 4.5.2) will be considered for the derivation of the primary efficacy variable.

- For those subjects with documentation of an unrefuted primary efficacy outcome event occurring  
after the date and time of randomization and up until the minimum (earliest) of the global rivaroxaban/aspirin outcomes cut-off date and the subject's last contact date during the rivaroxaban/aspirin portion of the study

time (in days) from randomization to the first occurrence of the primary efficacy outcome will be derived as:

- the date of the subject's first primary efficacy outcome event  
– the randomization date + 1.

This will constitute an uncensored observation.

- For those subjects without documentation of an unrefuted primary efficacy outcome event within the data scope according to intention-to-treat principle, time (in days) from randomization to the first occurrence of the primary efficacy outcome will be derived as:

 Text modified as per modification 1 in integrated SAP, Version 3.0.

 Text modified as per modification 1 in integrated SAP, Version 3.0.

 Text modified as per modification 1 in integrated SAP, Version 4.1.

 Text modified as per modification 1 in integrated SAP, Version 3.0.

- the minimum (earliest) of {the global rivaroxaban/aspirin outcomes cut-off date, the subject's last contact date during the rivaroxaban/aspirin portion of the study} – the randomization date +1.

This will constitute a right-censored observation.

### 6.2.1.2 Primary Efficacy Analysis

Analysis of the primary efficacy outcome will be based on the intention-to-treat principle. Two comparisons will be performed to compare each of the rivaroxaban-based treatment groups to the common aspirin-control group to evaluate:

- Superiority of rivaroxaban 2.5 mg bid + aspirin 100 mg od over rivaroxaban placebo + aspirin 100 mg od (control)
- Superiority of rivaroxaban 5 mg bid + aspirin placebo over rivaroxaban placebo + aspirin 100 mg od (control).

The primary null hypothesis  $H_{0;riva2.5}$ :

“There is no difference between the rivaroxaban 2.5 mg bid + aspirin 100 mg od treatment group and the rivaroxaban placebo + aspirin 100 mg od (control) in the probability of the primary efficacy outcome for all time points  $t \geq 0$  relative to randomization.”

will be tested against the alternative hypotheses  $H_{1;riva2.5}$ :

“There is a difference between the rivaroxaban 2.5 mg bid + aspirin 100 mg od treatment group and the rivaroxaban placebo + aspirin 100 mg od (control) in the probability of the primary efficacy outcome for at least one time point  $t \geq 0$  relative to randomization.”

The corresponding primary null hypothesis  $H_{0;riva5}$  will be tested comparing rivaroxaban 5 mg bid + aspirin placebo treatment with rivaroxaban placebo + aspirin 100 mg od (control). Statistical testing will be performed by a comparison of the “survival functions”  $S(t)$ , i.e., the probability that “time from randomization to the first occurrence of the following primary efficacy outcomes” is  $> t$ , for a time  $t$  relative to randomization.

The 2 comparisons will be performed using two separate stratified log-rank tests. Proton pump inhibitor use (3 strata levels: not randomized to a proton pump inhibitor; pantoprazole 40 mg od; pantoprazole placebo) will be used as a stratification factor in the statistical analysis. Study center will not be used as a stratification factor in the statistical analysis.

Following the mixture gatekeeping procedure as mentioned in Section 6.2, a truncated Hochberg test with the pre-specified truncation parameter  $\gamma = 0.9$  at  $\alpha=0.05$  will be used.

There will be no formal comparison between the rivaroxaban 2.5 mg bid + aspirin 100 mg od and rivaroxaban 5 mg bid + aspirin placebo groups.

---

 Text modified as per modification 1 in integrated SAP, Version 4.1.

Kaplan-Meier estimates of cumulative risk functions and Nelson-Aalen estimates of the cumulative hazard functions will be provided to evaluate the timing of event occurrence in the 3 antithrombotic study groups and the consistency of the respective treatment effects for all time points (the two survival curves in each comparison do not cross).

To derive the log-rank Z test statistic and the variance V of the log-rank statistics, SAS program code corresponding to the following will be used:

```

PROC LIFETEST DATA = <dataset> ALPHA=0.05 METHOD=KM NELSON;
  STRATA stratumn / GROUP=trtgrp TEST=(LOGRANK);61
  TIME ttevalue * ttecnsr(0);
RUN;

/*
where
dataset = name of sub-dataset including all ITT subjects randomized to
          respective rivaroxaban treatment group and control group
trtgrp   = variable coding randomized antithrombotic treatment group
          (0 = control group, 1 = rivaroxaban 2.5 mg + aspirin 100 mg)
ttevalue = time to first occurrence of primary efficacy outcome event
ttecnsr  = censoring index (0 = right-censored, 1 = event)
stratumn = variable for PPI stratification factor (three levels)
*/

```

Hazard ratio, relative risk reduction (RRR;  $RRR = 100 \times [1 - \text{hazard ratio}]%$ ), and corresponding 2-sided 95% confidence intervals will be estimated based on two separate stratified Cox proportional hazards models. Censoring will be assumed independent of the randomized group assignment.

For the analysis of the primary outcome in this study, the hazard function  $h(t)$  is the chance that an individual experiences an event of the primary efficacy outcome in the next instant in time, given that the individual has not had such an event up to time  $t$ . For example, for the comparison of rivaroxaban 2.5 mg bid + aspirin 100 mg od with rivaroxaban placebo + aspirin 100 mg od (control), the corresponding stratified Cox proportional hazards model can be described by the following equation:

$$h_k(t, x_i) = h_{0k}(t) \exp(\beta x_i),$$

where

- $h_k(\cdot)$  hazard function for primary efficacy outcome for stratum  $k$ ,  $k = 1, 2, 3$  ( $k$  represents PPI stratification factor), as a function of time and subject's covariates
- $h_{0k}(\cdot)$  unspecified underlying baseline hazard function for primary efficacy outcome per stratum  $k$ ; hazard of an individual with  $x_i = 0$
- $t$  time (in days) relative to the randomization date

 Text modified as per modification 3 in integrated SAP, Version 4.1.

$x_i$  antithrombotic treatment group of subject  $i$   
 (0 corresponds to “rivaroxaban placebo + aspirin 100 mg od (control)” and  
 1 corresponds to “rivaroxaban 2.5 mg bid + aspirin 100 mg od”)

$\beta$  unknown parameter (to be estimated); hazard ratio =  $\exp(\beta)$

SAS program code corresponding to the following will be used:

```

PROC PHREG DATA = <dataset>;
  MODEL ttevalue * ttecnsr(0) = trtgrpn / RL TIES=EFRON ALPHA=0.05;
  STRATA stratumn;
RUN;

/*
where
dataset = name of sub-dataset including all ITT subjects randomized to
          respective rivaroxaban treatment group and control group
trtgrpn  = variable coding randomized antithrombotic treatment group
          (0 = control group, 1 = rivaroxaban 2.5 mg + aspirin 100 mg)
ttevalue = time to first occurrence of primary efficacy outcome event
ttecnsr  = censoring index (0 = right-censored, 1 = event)
stratumn = variable for PPI stratification factor (three levels)
*/

```

Additional procedure options controlling the output may be added to the program codes.

### Sensitivity analyses

Sensitivity analyses will be performed to include all primary efficacy outcome events up until the minimum (earliest) of the Final rivaroxaban/aspirin Follow-up Visit date and the subject’s last contact date during the rivaroxaban/aspirin portion of the study.

In addition, the number of primary efficacy outcome events occurring after the Final rivaroxaban/aspirin Follow-up Visit until the rivaroxaban/aspirin Washout Telephone Visit, included in the clean database for the rivaroxaban/aspirin comparisons, will be summarized by rivaroxaban/aspirin study treatment group.

The plausibility of the proportional hazards assumption will be assessed by visually examining both the plot of the log of the negative log of Kaplan-Meier estimates of the survival function versus the log time for evidence of non-parallelism and the smoothed plot of the scaled Schoenfeld residuals to directly visualize the log hazard ratio (Grambsch and Therneau, 1994 [8]), for each stratum separately, and by including a time-treatment interaction term in the Cox model (time log transformed). The SAS code is adapted as follows:

 Text modified as per modification 1 in integrated SAP, Version 4.1.

```

PROC PHREG DATA = <dataset>;
  MODEL ttevalue * ttecnsr(0) = trtgrpnr trtltime / RL TIES=EFRON ALPHA=0.05;
  STRATA stratumn;
  trtltime = trtgrpnr*log(ttevalue);
RUN;

```

The significance of the interaction will be tested at the 5% type I error level. If the interaction is significant and there is strong evidence of non-proportionality from the plots, time-dependent hazard ratios will be estimated with the model that includes the interaction term.

### Analysis of the joint effect and/or interaction of study treatments

In addition, an analysis of the joint effect and/or interaction between rivaroxaban-based anti-thrombotic therapy and proton pump inhibitor use on the primary efficacy outcome will be performed for those subjects randomized to both antithrombotic and pantoprazole study medication. Joint effect and interaction between the antithrombotic and pantoprazole study groups on the primary efficacy outcome will be explored based on the intention-to-treat principle. The analysis will use two separate Cox proportional hazards models, one for the comparison of rivaroxaban 2.5 mg bid + aspirin 100 mg od vs. rivaroxaban placebo + aspirin 100 mg od, and one for the comparison of rivaroxaban 5 mg bid+ aspirin placebo vs. rivaroxaban placebo + aspirin 100 mg od.

The Cox proportional hazards model (e.g., for the comparison of rivaroxaban 2.5 mg bid + aspirin 100 mg od vs. rivaroxaban placebo + aspirin 100 mg od) can be described by the following equation:

$$h(t, x_{1i}, x_{2i}, x_{3i}) = h_0(t) \exp(\beta_1 x_{1i} + \beta_2 x_{2i} + \beta_{12} x_{1i} x_{2i}),$$

where

$h(\cdot)$  hazard function for primary efficacy outcome as a function of time and subject's covariates

$h_0(\cdot)$  unspecified underlying baseline hazard function for primary efficacy outcome

$t$  time (in days) relative to the randomization date

$x_{1i}$  antithrombotic treatment group of subject  $i$   
(0 corresponds to "rivaroxaban placebo + aspirin 100 mg od (control)" and 1 corresponds to "rivaroxaban 2.5 mg bid + aspirin 100 mg od")

$x_{2i}$  indicator variable for "pantoprazole 40 mg od treatment group",  
i.e.,  $x_{2i} = 1$  if subject  $i$  was randomized to pantoprazole 40 mg treatment,  
 $x_{2i} = 0$  if subject  $i$  was randomized to pantoprazole placebo

$\beta_1, \beta_2, \beta_{12}$  unknown parameters (to be estimated)

SAS program code corresponding to the following will be used:

 Text added as per modification 7 in integrated SAP, Version 3.0.

```
PROC PHREG DATA = <dataset>;
  MODEL ttevalue * ttecnsr(0) = trtgrp pn ppigrpn trtgrp*ppigrpn
    / RL TIES=EFRON ALPHA=0.05;
RUN;

/*
where
dataset = name of sub-dataset including all ITT subjects randomized to
          respective rivaroxaban treatment group and control group
trtgrp  = variable coding randomized antithrombotic treatment group
          (0 = control group, 1 = rivaroxaban 2.5 mg + aspirin 100 mg)
ppigrpn = indicator variable: ppilgrp = 1, if subject randomized to
          pantoprazole 40 mg treatment, else ppilgrp = 0,
          if subject randomized to pantoprazole placebo
ttevalue = time to first occurrence of primary efficacy outcome event
ttecnsr  = censoring index (0 = right-censored, 1 = event)
*/
```

If the interaction term for the two randomized treatments is significant at the 5% type I error level, then an interaction ratio will be calculated (McAlister et al., 2003 [15]) to describe the clinical significance of any synergy and sub-additivity of the two treatment effects on the primary efficacy outcome. For the comparison of rivaroxaban 2.5 mg bid + aspirin 100 mg od vs. rivaroxaban placebo + aspirin 100 mg od this means that the following two ratios are determined, where the cumulative event rate is determined including all events considered in the primary analysis.

- Ratio A:  
Cumulative event rate for the primary efficacy outcome for subjects randomized to both rivaroxaban 2.5 mg bid + aspirin 100 mg od and pantoprazole 40 mg od divided by cumulative event rate for the primary efficacy outcome for subjects randomized to both rivaroxaban placebo + aspirin 100 mg od and pantoprazole 40 mg od
- Ratio B:  
Cumulative event rate for the primary efficacy outcome for subjects randomized to both rivaroxaban 2.5 mg bid + aspirin 100 mg od and pantoprazole placebo divided by cumulative event rate for the primary efficacy outcome for subjects randomized to both rivaroxaban placebo + aspirin 100 mg od and pantoprazole placebo.

The ratio of ratio A and ratio B gives an estimate of the interaction ratio. Given the large sample size of this trial, a very small interaction may be detected that lacks clinical significance. An interaction ratio estimate of  $\leq 0.8$  (antagonism or sub-additivity) or  $\geq 1.25$  (synergy) will be considered “clinically significant”.

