## 6.2 Efficacy

Unless otherwise specified, all statistical tests will be interpreted at a 2-sided type I error level of  $\alpha = 0.05$  and all confidence intervals at a 2-sided level of 95%. Due to the conservative boundaries according to Haybittle – Peto used for interim analyses, no adjustment will be performed for the final primary efficacy analysis.

Primarily, for time-to-event analyses the censoring mechanism will be assumed to be non-informative due to an anticipated low non-cardiovascular death rate and almost complete follow-up for outcomes within this trial (according to expectations). Subjects will be handled as right-censored in primary time-to-event analyses. For the unexpected case that sensitivity analyses are needed, please refer to Section 6.2.7.

The trial success will be determined based on the totality of evidence for significance, magnitude, and direction of treatment effect from the analysis of primary and secondary efficacy outcomes.

The recommendation by the independent DSMB to stop the rivaroxaban/aspirin arms early due to overwhelming efficacy after the first interim analysis was guided by a modified Haybittle-Peto rule, expecting “a reduction of at least 4 standard deviations in the analysis of the primary efficacy outcome”. The 2-sided type I error level corresponding to this decision rule can be calculated via  $\alpha^* = \Phi(-4) + 1 - \Phi(4) = 0.0000633$ , where  $\Phi$  denotes the cumulative distribution function of the standard normal distribution. Considering the two comparisons, one for each rivaroxaban-treatment

---

[figure not shown]
 Text deleted as per integrated CSP, Version 3.0.

arm, being made according to this rule, the type I error level applied at the first interim analysis is about  $\alpha_1 = 2\alpha^* = 0.0001267$ .

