Therefore, the Cox proportional hazards model (e.g., for the comparison of rivaroxaban 2.5 mg bid + aspirin 100 mg od vs. rivaroxaban placebo + aspirin 100 mg od) can be described by the following equation:

$$h(t, x_{1i}, x_{2i}) = h_0(t) \exp(\beta_1 x_{1i} + \beta_2 x_{2i} + \beta_{12} x_{1i} x_{2i}),$$

where

$h(\cdot)$  hazard function for pantoprazole outcome as a function of time and subject's covariates

$h_0(\cdot)$  unspecified underlying baseline hazard function for pantoprazole outcome

$t$  time (in days) relative to the randomization date

$x_{1i}$  antithrombotic treatment group of subject  $i$   
 (0 corresponds to “rivaroxaban placebo + aspirin 100 mg od (control)” and  
 1 corresponds to “rivaroxaban 2.5 mg bid + aspirin 100 mg od”)

$x_{2i}$  pantoprazole group of subject  $i$   
 (0 corresponds to “pantoprazole placebo-control group” and  
 1 corresponds to “pantoprazole 40 mg od treatment group”)

$\beta_1, \beta_2, \beta_{12}$  unknown parameters (to be estimated)

SAS program code corresponding to the following will be used:

```
PROC PHREG DATA = <dataset>;
  MODEL ttevalue * ttecnsr(0) = trtgrp pn ppilgrp pn /
      RL TIES=EFRON ALPHA=0.05;
RUN;

/*
where
dataset = name of sub-dataset including all ITT subjects randomized to
          respective rivaroxaban treatment group and control group
trtgrp pn = variable coding randomized antithrombotic treatment group
            (0 = control group, 1 = rivaroxaban 2.5 mg + aspirin 100 mg)
ppilgrp pn = variable coding randomized pantoprazole treatment group
             (0 = pantoprazole placebo, 1 = pantoprazole 40 mg treatment)
ttevalue = time to first occurrence of pantoprazole outcome event
ttecnsr = censoring index (0 = right-censored, 1 = event)
*/
```

If the interaction term is significant at the 5% type I error level, then an interaction ratio will be calculated (McAlister et al., 2003 [15]) to describe the clinical significance of any synergy and sub-additivity of the two treatment effects on the pantoprazole outcome (see Section 6.2.1.2).

Additional exploratory analyses will include, e.g., a comparison of subjects who used proton pump inhibitor at baseline (and therefore were not randomized to receive pantoprazole 40 mg od or pantoprazole placebo) with subjects randomized to pantoprazole placebo group with regard to the pantoprazole outcome.

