### **5.2.6 Potential Modification of Rivaroxaban Treatment Effect by Pantoprazole**

The results of the Cox proportional hazards model including the effects of antithrombotic treatment, pantoprazole treatment, and the interaction of those have been reported for selected outcomes based on CDB1 to exclude an interaction effect between antithrombotic and pantoprazole treatment.

To further investigate if pantoprazole treatment has the potential to modify the rivaroxaban treatment effect on the following unrefuted outcomes

- Primary efficacy outcome
- Composite of MI, ischemic stroke, and CV death
- Secondary efficacy outcome
- Modified ISTH major bleeding
- Modified ISTH major bleeding in gastrointestinal tract
- GI bleeding (composite of the first three components of the GI outcome referring to upper GI bleeding),

these outcomes will be evaluated for the ITT analysis set by antithrombotic treatment groups in the rivaroxaban/aspirin follow-up data scope by depicting

- the number of subjects with event, crude incidences, incidence rates and Kaplan-Meier estimates in
  - the ITT analysis set
  - the pantoprazole treatment groups
    - pantoprazole 40mg od
    - pantoprazole placebo od
    - not randomized to pantoprazole/placebo
- the assessment of homogeneity of rivaroxaban treatment effect by the pantoprazole treatment groups (including subgroup-interaction p-value)
- forest plots for the above.

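### The 0.8/1.25 limits for a clinically significant rivaroxaban–pantoprazole interaction are used only after p<0.05, at event counts where they can filter nothing; the ratio and its CI should be reported regardless

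*SAP*

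**What the plan says.** For each rivaroxaban arm against aspirin control, SAP 4.1 section 6.2.1.2 (joint effect and interaction of study treatments) fits a Cox model with antithrombotic arm, pantoprazole arm and their product. The analysis "will be performed for those subjects randomized to both antithrombotic and pantoprazole study medication", so each model holds two of the three antithrombotic arms and leaves out subjects who were not randomized to pantoprazole or placebo.

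The next step is conditional on the interaction term being "significant at the 5% type I error level, then an interaction ratio will be calculated". The level is two-sided under the general rule in section 6.2 ("all statistical tests will be interpreted at a 2-sided type I error level of" 0.05). Ratio A compares cumulative event rates, rivaroxaban arm over control, among subjects on pantoprazole. Ratio B does the same among subjects on pantoprazole placebo. Then "The ratio of ratio A and ratio B gives an estimate of the interaction ratio", and a value of 0.8 or below, or 1.25 or above, counts as clinically significant. The reason given is: "Given the large sample size of this trial, a very small interaction may be detected that lacks clinical significance".

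Section 6.2.4.2 has the same condition for the pantoprazole outcome: "If the interaction term is significant at the 5% type I error level, then an interaction ratio will be calculated". Neither section gives power for the interaction test, says how a non-significant result is to be read, or sets a confidence interval against the limits.

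The later SAP for the pantoprazole close-out (PPI SAP), section 5.2.6, says that the interaction models from the first clean database (CDB1) were reported "to exclude an interaction effect between antithrombotic and pantoprazole treatment".

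**The concern.** A significance test followed by a relevance filter makes sense when the test is sensitive enough to flag effects too small to matter. If the test reaches significance only for ratios already outside 0.8–1.25, the filter never acts. The condition then works the other way: it withholds estimates that the SAP's own limits would mark as clinically significant.

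A ratio of 1.25 is not small here. With the planned 20% risk reduction under pantoprazole placebo, 0.80 × 1.25 = 1.00, so no rivaroxaban benefit is left under pantoprazole. At stake is whether an estimate of that size is set against the limits at all, and whether a non-significant p-value is mistaken for evidence that the two treatments do not interact.

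**Working it through.** **Inputs from SAP 4.1**
- Events at 2,200 in total: 826 control and 687 per rivaroxaban arm, so 826 + 687 = 1,513 per comparison (section 4.4).
- Looks at 50% (about 1,100 events) and 75% (about 1,650 events) of 2,200 (section 4.4). The rivaroxaban/aspirin arms stopped after the first look, with a cut-off of 06 February 2017.
- 27,400 subjects randomized; at least 16,440 to pantoprazole or placebo, 1:1 (section 7).
- Planned effect: 20% relative risk reduction (section 7).

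**Assumptions.** The event count at the cut-off is not given, so 50–100% of planned events is used. The share in the pantoprazole randomization is 16,440/27,400 = 60%. It is 16,440/21,400 = 77% if the 16,440, which the SAP attributes to protocol version 2.0, is read against that version's total. Events are taken as proportional to subjects.

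**Reproducing the plan's figures first.** The inputs were a 3.32% control rate, hazard ratio 0.80 on drug, the stated discontinuation and about 1% per year non-CV death, with the pace of accrual for the first 18,000 subjects assumed. They give 827 control and 687–688 rivaroxaban events (stated: 826 and 687). Power is 98.3–98.4% for at least one comparison and 93.0–93.1% for both (Table 7-3: 98.27% and 92.97%).

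**Formulas.** E = 1,513 × fraction of planned events × share. SE(log ratio) = √(Σ 1/events) over the four cells, split 1 : 0.8 : 1 : 1. Smallest significant ratio = exp(1.96 × SE). Power at 1.25 = Φ(ln 1.25/SE − 1.96), with ln 1.25 = 0.223.

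Example, 50% of events and 60% share: E = 1,513 × 0.5 × 0.6 ≈ 454; cells about 119/96/119/119; SE = 0.189; exp(1.96 × 0.189) ≈ 1.45; power 22%.

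| Planned events | Share | E | SE | Smallest significant ratio | Power at 1.25 |
|---|---|---|---|---|---|
| 50% | 60% | 454 | 0.189 | 1.45 (0.69) | 22% |
| 75% | 60% | 681 | 0.154 | 1.35 (0.74) | 31% |
| 100% | 60% | 908 | 0.133 | 1.30 (0.77) | 39% |
| 50% | 77% | 581 | 0.167 | 1.39 | 27% |
| 75% | 77% | 872 | 0.136 | 1.31 | 37% |
| 100% | 77% | 1,162 | 0.118 | 1.26 (0.79) | 47% |

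Every threshold lies outside 0.8–1.25. With SE ≈ 4/√E, an estimate of exactly 1.25 reaches p = 0.05 only at E = 16 × (1.96/0.223)² ≈ 1,234. Power of 80% needs about 2,522 events in the model.

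**How often the condition blocks a relevant estimate.** If the true ratio is 1.25, the estimate is at or above 1.25 but non-significant in about 28% of trials at E = 454, 19% at 681, 11% at 908 and 2% at 1,162.

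**Pantoprazole outcome (6.2.4.2).** Take 570–780 events, a 50% risk reduction and two thirds of events in two antithrombotic arms, so E = 380–520. The smallest significant ratio is 1.43–1.52 and power at 1.25 is 18–23%.

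**Two notes.** The SAP's ratio uses cumulative event rates rather than exp(β12). With about 9% of control subjects having an event (826/9,134), the two should be close, which is why the conclusion says 'materially'. The SAP also labels 1.25 and above as synergy, although for an adverse outcome it means less rivaroxaban benefit under pantoprazole. The arithmetic does not depend on the label.

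**The case against.** Four points stand.

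- **The question is not left unexamined.** The interaction model is fitted unconditionally in SAP 4.1. PPI SAP 5.2.6 adds event rates, Kaplan-Meier estimates, a homogeneity p-value and forest plots by pantoprazole group for six outcomes, with no p-value condition. PPI SAP 5.2.5 gives pantoprazole hazard ratios with 95% CIs within each antithrombotic arm. Only the ratio and its limits are gated.
- **A reader might infer that a non-significant test will be declared proof of no interaction.** No section sets that rule. The wording about excluding an interaction is one retrospective remark in 5.2.6, and the text that follows investigates the question further.
- **A reader might also infer that pooling over the pantoprazole factor rests on this test.** It does not. The primary log-rank test is stratified by PPI group in any case, and no alpha or success criterion depends on the interaction result.
- **The low power belongs to one scenario: 0.80 under placebo and 1.00 under pantoprazole.** If 0.80 is the average on the log scale (1.00 and 0.64), the ratio is 1.00/0.64 = 1.56 and power is about 65–91% at a 60% share. If pantoprazole cancelled the effect in both rivaroxaban comparisons, at least one test would be significant in about 34–55% of trials at that share.

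It can also be said that ungated estimates stray outside the limits by chance: with no interaction, about 23% of the time at E = 454 and 9% at E = 908. That is a reason to show the confidence interval rather than to keep the condition.

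None of this rescues the stated rationale or makes the limits do any work, because the added displays contain neither the ratio nor the limits.

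**Conclusion.** The ordering of steps in 6.2.1.2 and 6.2.4.2 is badly fixed, and its stated reason is wrong on the plan's own event numbers. For the primary outcome the smallest significant ratio is about 1.26–1.45 over the assumed ranges. The limits therefore filter nothing, and estimates from 1.25 up to that threshold (or from 0.8 down to about 0.69–0.79) are not assessed against them. Power at a ratio of 1.25 is about 22–47% per comparison, on the reading of 0.80 under placebo and 1.00 under pantoprazole.

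For the pantoprazole outcome the same ordering problem holds, but a ratio of 1.25 turns a hazard ratio of 0.50 into 0.625 and cancels nothing.

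The point does not go further than this. The documents do not support saying that effect modification goes unassessed, that interaction is formally declared absent, or that the primary analysis is at risk. It is a modest but worthwhile correction to the reporting of an exploratory analysis.

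**What to change.** - In 6.2.1.2 and 6.2.4.2, delete the p<0.05 condition; in 6.2.1.2 also delete the sentence about detecting a very small interaction. Substitute wording such as: *The interaction ratio exp(β12) and its 95% confidence interval will be reported for both rivaroxaban comparisons whatever the p-value, and shown against the limits 0.8 and 1.25. A non-significant interaction test does not show that interaction is absent.*
- In PPI SAP 5.2.6, change the stated purpose of the CDB1 models from excluding an interaction effect to exploring one.
- Do not add a rule that the whole CI must lie inside the limits to exclude an interaction, or wholly beyond one to declare it. The exclusion part needs about 1,234 events in the model, and even the most favourable case has about 1,162 (half-width 1.96 × 0.117 = 0.230 against 0.223). The declaration part needs an estimate of about 1.25 × 1.45 = 1.81 at 454 events or 1.25 × 1.30 = 1.62 at 908. It would flag fewer interactions than the present rule.

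The cost is wording only, since β12 comes from a model already planned. The price is that the result will mostly have to be described as imprecise.

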## 2. Study Objectives

### Primary objective for rivaroxaban randomization

- To determine whether rivaroxaban 2.5 mg bid + aspirin 100 mg od compared with aspirin 100 mg od reduces the risk of a composite of myocardial infarction, stroke, or cardiovascular death in subjects with CAD or PAD
- To determine whether rivaroxaban 5 mg bid compared with aspirin 100 mg od reduces the risk of a composite of myocardial infarction, stroke, or cardiovascular death in subjects with CAD or PAD

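### SAP 6.2.1.2: read as A/B, the interaction ratio carries reversed direction labels, so a weaker rivaroxaban effect with pantoprazole would be called synergy

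*SAP*

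**What the plan says.** The subsection of 6.2.1.2 on the joint effect and interaction of study treatments fits a Cox model with antithrombotic group, pantoprazole group and their product. Pantoprazole is coded 1 and its placebo 0. If the product term is significant at 5%, two ratios are formed (shown for the 2.5 mg comparison).

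- Ratio A has as numerator the "Cumulative event rate for the primary efficacy outcome for subjects randomized to both rivaroxaban 2.5 mg bid + aspirin 100 mg od and pantoprazole 40 mg". Its denominator is the same rate in subjects "randomized to both rivaroxaban placebo + aspirin 100 mg od and pantoprazole 40 mg od".
- Ratio B is the corresponding ratio without active pantoprazole. Its denominator is the rate in subjects "randomized to both rivaroxaban placebo + aspirin 100 mg od and pantoprazole placebo".

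The SAP then states: "The ratio of ratio A and ratio B gives an estimate of the interaction ratio". It gives no formula. An estimate at or below 0.8 ("antagonism or sub-additivity") or at or above 1.25 (synergy) is to be considered clinically significant.

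Section 2 fixes the direction of benefit: the objective is to show that each rivaroxaban regimen "compared with aspirin 100 mg od reduces the risk of a composite of myocardial infarction, stroke, or cardiovascular death". Section 6.2.4.2 refers back to this rule for the gastrointestinal outcome, "to describe the clinical significance of any synergy and sub-additivity of the two treatment effects on the pantoprazole outcome".

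**The concern.** A and B are ratios of adverse-event rates, so a value further below 1 means a larger benefit. If A exceeds B, rivaroxaban prevents fewer events with pantoprazole than without it, and A/B is above 1. In ordinary use that is antagonism or sub-additivity of the two treatments, but the SAP calls it synergy once it reaches 1.25. The opposite case is mislabelled in the same way.

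This is the only place in the integrated SAP that attaches a direction word to a factorial interaction on the primary outcome. The question matters to the trial: the later pantoprazole SAP (Section 2) makes it an objective to determine whether pantoprazole modifies the antithrombotic effect. A report that used the labels as written could tell readers that the drugs reinforce each other when the data showed the reverse.

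**Working it through.** **Inputs.** Definitions of A and B, the 5% condition and the thresholds 0.8 and 1.25: SAP 6.2.1.2. Planned effect, 20% relative risk reduction: Section 7. Control incidence, about 3.3% per year: Section 7. Expected events, 826 (control) and 687 (each rivaroxaban arm): Section 4.4.

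**1. The thresholds.** 1/0.8 = 1.25 exactly. The cut-offs are symmetric on the log scale, so inverting the ratio selects the same interactions.

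**2. The direction.** Let R be the cumulative event rate.

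Interaction ratio = A/B = [R(riva, panto) / R(control, panto)] / [R(riva, placebo) / R(control, placebo)]

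The hazard-scale counterpart is exp(β12) in the SAP's Cox model, because pantoprazole is coded 1. Take B = 0.80, the planned effect:

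| Situation with pantoprazole | A | A/B | SAP label | Correct direction |
|---|---|---|---|---|
| Benefit lost | 1.00 | 1.25 | synergy | antagonism |
| Net harm | 1.10 | 1.375 | synergy | antagonism |
| No interaction | 0.80 | 1.00 | none | none |
| Larger benefit | 0.64 | 0.80 | antagonism | synergy |
| Larger benefit | 0.60 | 0.75 | antagonism | synergy |

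A main effect of pantoprazole cancels within A. With both pantoprazole event rates multiplied by 0.9, every A/B above is unchanged.

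**3. The inverse.** B/A for complete loss of benefit is 0.80/1.00 = 0.80, and for A = 0.64 it is 0.80/0.64 = 1.25. Only in that order do the labels fit.

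**4. How readily the threshold is reached.** Complete loss of the planned benefit lies close to the boundary:

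- On cumulative rates at 3.3% per year, with the hazard ratio moving from 0.80 to 1.00, A/B = (1 − exp(−0.033T)) / (1 − exp(−0.8 × 0.033T)). This is 1.242, 1.238 and 1.234 at T = 2, 3 and 4 years, just under 1.25.
- With the expected event counts and equal arms, B = 687/826 = 0.832. Complete loss then gives 1/0.832 = 1.20, and A must reach 0.832 × 1.25 = 1.04 before the label applies.

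**5. What the 5% condition requires.** Assume that events divide equally over the four cells, so SE(log ratio) = √(16/d). Here d is the number of events in the two compared arms among subjects randomised to pantoprazole or placebo. The two arms hold 1,513/2,200 of all events. The pantoprazole share is taken as 16,440/27,400 = 0.60, or as 16,440/21,400 = 0.77, because Section 7 attributes the 16,440 to the protocol version that had the smaller total. The smallest significant ratio is exp(1.96 × SE):

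| Total events | Share | d | Smallest significant ratio |
|---|---|---|---|
| 1,100 | 0.60 | 454 | 1.44 |
| 1,100 | 0.77 | 581 | 1.38 |
| 2,200 | 0.60 | 908 | 1.30 |
| 2,200 | 0.77 | 1,162 | 1.26 |

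The 5% test is therefore the binding condition. A ratio that passes it would, to this approximation, also pass 1.25 (or 0.8 in the other direction), so a direction label would nearly always follow.

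**The case against.** **The order of division is not written as a formula.** If B/A was meant, the labels are right. This stands as a limit on what can be said about intent. The source cited for the method is not at hand and does not settle it. But A/B is the natural reading and agrees with the model coding. Under the other reading the stated ratio is what needs correcting, so the text must change either way.

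**The classification is not affected.** A reader might infer that the wrong interactions would be declared clinically significant. The documents do not support that: the thresholds are reciprocal, and a value beyond either one is declared significant under both orders. No later decision in the SAP depends on the direction word, and ratios A and B are both determined, so an attentive reader could recover the direction.

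**The rule is conditional and exploratory.** A reader might infer that any loss of benefit would be reported as synergy. It would not: the 5% test and a threshold must both be met, and complete loss of the planned effect only about reaches 1.25. The stratified log-rank tests, the gatekeeping procedure and the sample size are unaffected.

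**A ratio above 1 can be called synergy for two risk factors.** That usage would fit if rivaroxaban raised the event rate. It does not fit an outcome that the treatment is meant to reduce.

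**The gastrointestinal outcome.** A reader might extend the reversal to Section 6.2.4.2. That goes too far. There the difficulty is different: pantoprazole is meant to lower the event rate while rivaroxaban may raise bleeding, so the labels have no clear meaning. The later pantoprazole SAP (Section 5.2.3) restates that interaction analysis without the ratio or the labels. It is to be read together with version 4.1 and does not expressly withdraw the rule.

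**Conclusion.** The point holds for the primary outcome in Section 6.2.1.2. Read as A/B, both direction labels are the wrong way round for an adverse outcome that rivaroxaban is meant to reduce. If the interaction test is significant and a threshold is crossed, the direction reported from the label would be wrong, while the finding of clinical significance itself would be unchanged. The conclusion rests on two assumptions: that the ratio is A divided by B, and that benefit means fewer events. It is an error in an interpretation rule for an exploratory analysis and does not bear on the primary inference. The gastrointestinal cross-reference is a secondary matter of unclear wording and applies only if the ratio is still used there.

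**What to change.** In Section 6.2.1.2, write the interaction ratio as A/B, note that it corresponds to exp(β12), and relabel: 0.8 or less is synergy (larger risk reduction with pantoprazole); 1.25 or more is antagonism or sub-additivity (smaller risk reduction with pantoprazole). Equivalently, define the ratio as B/A and keep the present labels.

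If the ratio is still used for the gastrointestinal outcome, replace the labels there with a plain statement: below 1, the rivaroxaban-to-aspirin event ratio is smaller with pantoprazole; above 1, it is larger.

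The cost is about two sentences of SAP text. No threshold or data collection changes. Keeping A/B needs no programming; choosing B/A means only inverting one quotient. If a report has already used the labels, its wording should be checked against A and B.
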